Official title: A Randomized Trial Examining Plasma Exchange using the BD Catheter In an Outpatient Apheresis Unit (REPLACE)

NCT number: NCT04253756 IRB Approved date: 4/22/2020 A Randomized Trial Examining Plasma Exchange using the BD Catheter In an Outpatient AphCresis Unit (REPLACE)

PI: [name] [name], CMSRN, QIA

Faculty Sponsor: [name] MD

Co-Investigator: [name], RN

Research manager: [name] PhD

Date: 11/27/2019

Version: 1

Introduction and Purpose

Nurses and apheresis technicians caring for patients requiring therapeutic apheresis procedures (TAP) utilize a wide range of intravenous catheters to obtain the access required to perform their procedures(Kalantari, 2012), (Golestaneh & Mokrzycki, 2013). The standard of care for our facility is to use an 18-gauge apheresis needle (Medisystems®) for the access site and an 18-gauge autogard catheter for the return site. Unfortunately, there is minimal literature defining best practices for catheter size selection(Salazar et al., 2017). At UT Southwestern Medical Center, our goal is to provide peripheral therapy to reduce the need for central access, such as a medical ports or tunneled catheters(Spires et al., 2018). However, the requirement for an 18 gauge catheter for an adequate return site, at times, rules out the patient for peripheral therapy(Putensen, Leverett, Patel, & Rivera, 2017). This requires central venous access to be obtained, which can delay the start of the procedure.

The lack of scientific evidence to support the use of smaller peripheral return catheters has increased the use of implanted ports in our institution(Putensen et al., 2017). The objectives of our pilot study are patient-centered and include analyzing the safety of using smaller peripheral return catheters without increasing the risk of hemolysis.

Background and Significance

TAP treats a wide range of disease processes and, in all cases, requires inlet and return venous access to perform the procedure. The goal of TAP is to return the patient to baseline and maintain independence and function. A larger needle (18 gauge) can cause more discomfort to the patient as well as additional scarring. A smaller needle may present less discomfort and scarring to the patient. Our goal in our outpatient clinic is to minimize disruption to the patient's routine and help them maintain normal activities of daily living.

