To accomplish these goals, our outpatient clinic is open Monday thru Friday offering 4 different appointment times. All patients that are referred to our clinic for TAP, first receive a vein evaluation to see if the patient is a candidate for peripheral IV therapy. At our clinic, approximately 68% of our TAP's are performed peripherally. This eliminates the risk of a central line infection and any alteration in activities of daily living, such as bathing(Kramer, 2016), (Shang, Ma, Poghosyan, Dowding, & Stone, 2014),(Keller et al., 2018; McDiarmid, 2015).

Our hypothesis, is that the 20-gauge BD Nexiva Diffusics catheter provides the same efficacy as current practice with no increase in adverse events for patients undergoing therapeutic apheresis. The results from our study will be significant because if the 20 guage needle is equally effective for TAP, it can increase the number of patients that would be candidates for peripheral therapy. Therefore, decreasing the need for central venous access, which place the patient at an increased risk of infection. Our study is a comparison of 2 types of infusion catheters. The standard of care is an 18-gauge autogard catheter (control group) which will be compared to the 20-gauge BD Nexiva Diffusics (intervention).

- P patients who require therapeutic apheresis procedures (TAP)
- I use of 20G BD diffusics catheter during apheresis
- C use of 18 G standard of care IV catheter during apheresis
- O no difference in efficacy and no increase in safety events

Concise Summary of Project

This is a randomized pilot study of TAP using the current standard of care catheter (SOC) vs the BD Nexiva Diffusics Catheter. It is a single blinded, randomized study. Data will be used to refine and power a full randomized control trial. For this study, a sample of 33 encounters in each group (total of 66 encounters). Our specific aim is to test the hypothesis that the 20-gauge BD Nexiva Diffusics Catheter provides the same efficacy and lower pain level with no increase in adverse events for patients undergoing apheresis treatments.

Randomization Procedure

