Measures of Quality of Apheresis will include inlet rate, and return pressures, procedure time. These measures are all readily available in the electronic medical record (EMR) and are all currently recorded as standard of care. The inlet rate is defined as the percent of patient inlet rate divided by the maximum allowable inlet rate. Because inlet rates are different for each type of TAP has a different maximum inlet rate, this will allow standardization across procedures. The max inlet rate for Photopheresis is 50ml/sec, the max inlet for plasma exchange is 100ml/sec inlet for red blood cell exchange is 55ml/sec. In addition, the inlet rate for each participant in the intervention arm will be compared to the average of their last 5 procedures. This measure will compare the efficiency of the SOC verses the intervention.

Inclusion Criteria

- Adult (≥ 18 years old)
- Speaks and reads English
- A patient of the Apheresis clinic at UT Southwestern University Hospital and Clinics
- Scheduled to receive TAP (therapeutic plasma exchange, red blood cell exchange and extracorporeal Photopheresis) as standard of care

Exclusion Criteria

- Prisoners
- Persons under the age of 18 years
- Patient who are actively involved in chemotherapy

Sources of Research Material

There are three sources of data for this study: electronic medical record (EMR) and paper-and-pen data collection from the patient's bedside (Data Collection form), and lab results provided by the UTSW laboratory via EMR. The EMR data that will be collected will include demographic information such as: age, sex, race, ethnicity, and admission diagnosis. The paper-and pen-data collection will include the patient self-reported pain level (VAS Scale), CBC collection, procedure data (minutes, inlet rate, return line pressures and alarms) total procedure time and post procedure sample. The paper-and-pen data collection form (Appendix 1) will record data only during patients TAP's encounter. Blood sample will be obtained from a SOC line. An additional 8 ml's for blood will be drawn from the patients for research purposes. Results from the bloodwork will be provided by the UTSW laboratory via the patient's EMR.

Recruitment Methods and Consenting Process

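### Inlet rate: the only comparison spelled out sets 20G encounters against the patient's own earlier procedures; the randomised 20G versus 18G comparison is not specified and the five-procedure window is undefined

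*Combined protocol and SAP*

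**What the plan says.** The paragraph on measures of apheresis quality, just before Inclusion Criteria, expresses inlet rate as a percentage of the maximum for the procedure type, because "this will allow standardization across procedures". It then gives one concrete comparison: "In addition, the inlet rate for each participant in the intervention arm will be compared to the average of their last 5 procedures". The next sentence states the aim: "This measure will compare the efficiency of the SOC verses the intervention". Of inlet rate, return pressures and procedure time it says "These measures are all readily available in the electronic medical record (EMR) and are all currently recorded as standard of care". Catheter type is not in that list.

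Other sections bear on how this can be read:
- Introduction and Purpose gives the facility standard as "an 18-gauge autogard catheter for the return site".
- Randomization Procedure re-randomises the patient at each encounter, up to 10 times.
- Study procedure has inlet rate recorded every 15 minutes at every study encounter, in both groups.
- The Statistical Analysis Plan names by-group ANOVA for plasma hemoglobin, procedure minutes and adverse events, and a chi-square analysis of return pressure by lumen occupancy. Inlet rate appears in none of these. Only the general descriptive summary of each variable would cover it.

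**The concern.** The stated aim is to compare standard of care with the intervention, yet the one comparison described does not use the randomised 18G encounters as its comparison group. It sets 20G encounters against the same patient's past. Any change over time in the patient, the veins or clinic practice would then be mixed with the catheter effect. The randomised comparison is protected against this.

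The reference itself is not fixed. The text does not say whether the five procedures precede enrolment or each encounter, whether study encounters count, whether they must be 18G, peripheral or of the same type, or what happens with fewer than five. Two analysts could follow the sentence and report different numbers.

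This matters somewhat because Potential Risks names a slower inlet rate as the route to longer procedures, and the pilot is meant to refine and power a full trial. The randomised difference in inlet rate would be useful for that.

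**Working it through.** The plan gives no figure for inlet rate, so there is none to reproduce. The check is of the text first, then of how far an undefined window could matter.

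**Text.** "In addition, the inlet rate for each participant in the intervention arm will be compared to the average of their last 5 procedures" begins as an addition to something, and rescaling to a percentage of maximum makes sense for a comparison between groups. "This measure will compare the efficiency of the SOC verses the intervention" points the same way, although its subject may be inlet rate in general or the five-procedure contrast. No sentence names a by-group model, test or per-encounter summary for inlet rate. By contrast, Study procedure says outright that the pain scale serves to compare the two groups. Because randomisation is by encounter, a patient can contribute to both groups; the intervention arm is read here as the 20G encounters.

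**Inputs.** 33 encounters per group, 66 in total (Concise Summary of Project); 30 expected participants (Recruitment Methods and Consenting Process); at most 10 encounters per patient (Randomization Procedure). Assumed: procedures before the study were all 18G, no off-study procedures fall between study encounters, and there are no switches or removals. Switches and removals (Potential Risks) and off-study 18G procedures would all lower the shares below.

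**Fixed window before enrolment, 18G only.** The 20G share of the reference is 0%.

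**Rolling window.** Given that the current envelope is 20G, any other envelope is 20G with probability 32/65 = 0.4923. At a patient's k-th study encounter, min(k−1, 5) of the five reference procedures are study encounters, so the expected 20G share is min(k−1, 5)/5 × 0.4923. This is 0 at k = 1, 0.0985 at k = 2 and 0.1969 at k = 3.

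- Even spread over 30 patients (24 × 2 + 6 × 3 = 66, average 66/30 = 2.2): (30 × 0 + 30 × 0.0985 + 6 × 0.1969)/66 = 0.063.
- Concentrated (4 × 10 + 26 × 1 = 66): one patient with 10 encounters contributes (0+1+2+3+4+5+5+5+5+5)/5 × 0.4923 = 3.446, so 4 × 3.446/66 = 0.209.
- Extreme, 7 patients (6 × 10 + 1 × 6 = 66): the patient with six contributes (0+1+2+3+4+5)/5 × 0.4923 = 1.477, so (6 × 3.446 + 1.477)/66 = 0.336.

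With no time trend, a constant 20G minus 18G difference would on average be read at 1 minus the share: about 94%, 79% and 66% of its true size. Only the first case uses the protocol's participant number with an even spread. The second keeps 30 patients but puts 40 of the 66 encounters in four of them; the third departs from the 30 expected.

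**Time trend.** No section gives a drift in inlet rate over visits, so the bias of the before-after contrast cannot be sized from the documents. It may be nil.

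**The case against.** The best reply is that the by-group comparison is already intended: inlet rate is collected in both groups, rescaled for comparability and said to compare the two catheters, and the five-procedure contrast is offered as a supplement. That largely stands. What remains is that the SAP does not say so, and the contrast that is described is the weaker one.

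A second reply is that the natural reading of the reference is a fixed set of 18G procedures, given the stated aim and the facility standard. That too is the likelier reading, and under it no 20G encounter enters. It still has to be written down.

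A third is that the historical contrast may be the more precise. Each patient serves as their own control against an average of up to five procedures, whereas at about 2.2 encounters each many patients will give few within-patient 20G and 18G pairs. This is a sound reason to keep it as supportive.

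A reader might go further and infer that the trial has given up its randomised comparison, that the reference is contaminated, or that the efficacy conclusion is biased. The documents support none of these. The randomised readings are collected regardless, contamination arises only under a rolling window, and inlet rate is not one of the SAP's two efficacy variables. Procedure minutes, on which a slower inlet rate would act, are compared by group.

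**Conclusion.** The point holds as a low-severity, cheap improvement. Two gaps are plain from the text: no by-group analysis of inlet rate is specified, and the five-procedure reference has no date, catheter, access-route or procedure-type limit. Following the described contrast literally gives a one-arm, non-randomised comparison.

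The size is modest. The expected 20G share of the reference is 0% with a fixed 18G window and about 6% with a rolling window at 30 evenly spread participants. The 21% and 34% figures need encounters concentrated in few patients and should not be taken as expected values. All three rest on the simplifying assumptions listed in the working. The primary conclusions are unaffected, and because the data will exist in any case, nothing is lost if the SAP is amended before analysis.

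**What to change.** In the SAP, state that inlet rate (the mean of the 15-minute readings, as a percentage of the procedure-type maximum) is compared between randomised 20G and 18G encounters as assigned, with a patient random intercept and procedure type as covariate. Take the assignment from the envelope and SID key, because the catheter field in Appendix 1 does not say whether it means assigned or used. Report how many 20G encounters were switched to 18G; the form has no field for this, so a note under Comments may be needed.

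Keep the five-procedure contrast as supportive. Limit its reference to up to five pre-enrolment, peripheral, 18G procedures of the same type, where the EMR shows this. Use those available if there are fewer than five, and report how many patients have none. These limits are needed because no eligibility criterion requires earlier procedures, and only about 68% of the clinic's procedures are peripheral. The protocol does not say that past catheter type is in the EMR; if it cannot be retrieved, say so.

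The cost is a few SAP sentences, one clarified protocol sentence and a little more analysis. The standard error will probably be wider than that of the historical contrast. As-assigned analysis also brings some dilution from readings taken after a switch. For illustration only, if 5% to 20% of 20G encounters switched and 25% to 75% of their readings came afterwards (assumed, with equal numbers of readings per encounter), 0.05 × 0.25 = 1.3% to 0.20 × 0.75 = 15% of 20G-group readings would be on 18G.

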After an eligible participant is consented to the study the patient will be randomized without replacement to the use of one of the two catheters. Using a random number generator, numbers between (1-66) were randomly divided into two groups: SOC Control group and BD Intervention group (Figure 1). A study identification number (SID) key will be saved on a UTSW approved secure device and only the research coordinator will have access to the SID key showing which SID coordinates with each group. This will ensure that unblinding can occur is necessary and there is a backup to randomization.

The research coordinator will have 66 randomized envelops without replacement. Half of the envelops will be assigned to 18G catheter SOC (control) and the other half be assigned to

20G BD Nexiva Diffusics catheter (intervention). The PI will be blinded, therefore the PI will pick an envelope when patients are consented and ready for treatment. Participants will be randomized after they have consented to the study. Participants' will then be randomized to one of the two groups again at each encounter (i.e., SOC visit). Inside the envelope it will tell the investigator if the patient is in the control or intervention group of the study.

To promote a more representative sample, each patient may participate a maximum of 10 times.

Study procedure:

[figure not shown]
Each enrolled patient will participate in the study will be randomized at each encounter. During each encounter the following information will be captured:

- 1. CBC
- 2. Patient discomfort

level with placement of catheter

- 3. Inlet rate
- 4. Return line pressures
- 5. Procedures alarms
- 6. Procedure total time
- 7. Post procedure sample

Treating nurse (RN) will start the TAPs procedure with one of the 2 catheters. During the intervention period, the RN will be at bedside during as it is SOC in the Apheresis unit however for the purpose of this study the RN will have the study data collection form (DCF, Appendix1). The RN will complete the pre-assessment including a pain assessment to establish pain level prior to procedure that is currently documented in the electronic medical record. The patient will be asked to self-report the pain level after the return line has been started on the visual analog scale (VAS) Scale from 0mm to 100mm "0 being the lowest/ no pain, 100mm being the highest

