level of pain". The VAS scale will be used for both the SOC and intervention group to compare the pain level when starting the return line. The RN will collect a CBC before the start of the procedure which will be used in the programing of the TAP procedure. The RN will start recording the "inlet rate, return line pressures, and alarms" every 15 minutes until the procedure is completed.

Before patient disconnects, and after the completion of procedure sing the same therapeutic apheresis procedure access site, a blood sample will be drawn by the RN 2 lavender top tubes (4ml) for plasma hemoglobin test. The plasma hemoglobin test will be sent to the UTSW lab for analysis of hemoloysis and results will be sent back directly to the PI. Blood sample results will be collected by the PI or the study team in an excel spreadsheet (CRF) that will be saved on a secure drive on the UTSW campus.

Hemolysis is defined as the destruction of red blood cells which leads to the release of hemoglobin from the red blood cells into the blood plasma. Each patient will be tested for hemolysis by running plasma hemoglobin test after the procedure has finished. This will be collected in a two lavender tops (4ml) The cost for this test is covered by sponsor and because the patient has an indwelling access to venous blood there will no charge for drawing the sample.. There is no clinical suspicion that the use of the 20-gauge BD Nexiva Diffusics Catheter will increase this risk. Hemolysis will be scored dichotomously as present or absent for each encounter.

Pain is defined as any increase discomfort experienced by the patient associated with the apheresis procedure. The current standard of care is to ask the patient "are you having pain" and then ask them to rate the pain from 0 to 10. For this study, one additional question will be asked after the patient's vein has been accessed (IV catheter in place). The patient will self-report their pain using a 100 mm VAS scale. "*The VAS has been used by healthcare providers to measure the characteristics of disease severity in each patient individually*"(Klimek et al., 2017) Currently, all peripheral apheresis patients have some pain/discomfort while having a treatment, however; it is usually tolerated with minimal complaints.

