be replaced with the SOC 18-gauge catheter. Obtaining blood samples may cause some discomfort, feeling lightheaded, fainting, bruising, clotting, and bleeding from the site of the needle stick and, in rare cases, infection. The risks are mitigated by drawing blood from a line that has already been established as part of SOC.

There is a low risk of breach in confidentiality. Subjects will be assigned individual study identification (SID) numbers and no personal identifiers will be included in the final summary.

Patients who are randomized to the 20-guage needle group and who fail the intervention will be given the 18-guage standard of care needle. At the patient's next visit, the patient will once again be randomized. If the patient is randomized into the 20-guage needle arm and fails the intervention a second time, the patient will be removed from the study.

Procedures to Maintain Confidentiality

Study participants will be given a study identification (SID) number. Only the approved study personnel and the principal investigator have access to the database linking the SID to the patient name. This database is kept on a protected drive on a password protected computer. Paper or hard copy participant records will be kept in a locked file cabinet in a locked office. If any identifying information is transmitted, it will be done so via secure e-mail and/or dedicated fax machines.

Statistical Analysis Plan

All data will be first collected on the DCF (Appendix I) and then entered into an electronic spreadsheet (e.g., MS Excel) which will be converted to SAS v 9.4 for analysis. All statistical analyses will be performed at UTSW in a location with secure data encryption capability. Initially, the data will be summarized first using standard measures of central tendency (mean, median, standard deviation, and interquartile range) for each variable. These will be examined to support the assumption of being approximately normally distributed. Baseline characteristics will be summarized using appropriate parametric and non-parametric measures.

The primary hypothesis is that the 20-gauge BD Nexiva Diffusics catheter provides the same efficacy of current practice with no increase in adverse events for patients undergoing therapeutic apheresis. This will be examined in 2 steps. First, ANOVA will be used to explore

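### Return-site harms that appear after the encounter have no route into the adverse-event comparison, and no rule ties a late event to the catheter that preceded it

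*Combined protocol and SAP*

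**What the plan says.** - **Recording window.** Sources of Research Material says of the data collection form that it "will record data only during patients" apheresis encounters. Under Study procedure, the nurse records machine data "every 15 minutes until the procedure is completed". The last study item is a blood sample taken before the patient is disconnected.
- **Route of the data.** The Statistical Analysis Plan states: "All data will be first collected on the DCF". The medical record is also a source, but the content described for it is demographics, admission diagnosis and laboratory results.
- **Re-randomisation.** Under Randomization Procedure, participants "will then be randomized to one of the two groups again at each encounter", to a maximum of 10 participations per patient. After a failed 20G encounter, Potential Risks says: "At the patient's next visit, the patient will once again be randomized".
- **Safety claim.** The primary hypothesis in the Statistical Analysis Plan includes the absence of excess adverse events with the 20G catheter. It is to be tested by comparing mean adverse-event counts between groups.
- **Site harms named.** Potential Risks lists "bruising, clotting, and bleeding from the site of the needle stick and, in rare cases, infection", as risks of drawing the blood sample. Background and Significance offers a possible benefit of gauge: "A smaller needle may present less discomfort and scarring to the patient".
- **Not described anywhere.** There is no contact after the visit, site check at the next visit, adverse-event window or rule for assigning a late event to an encounter.

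**The concern.** Two gaps combine here. The first is capture. If recording stops when the procedure ends and only the form feeds the analysis, the safety comparison rests on what can be seen while the patient is still in the chair. Some harms at a venous site can appear later. That is a general clinical assumption, since the documents give no timing.

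The second is attribution. The unit of randomisation is the encounter, so the same patient can have one catheter at one visit and the other at the next. The form in Appendix 1 carries one date, one study number and one catheter type. A problem from an earlier site that happens to be noticed at the next visit would have to be written on a form labelled with the new catheter, or left out. Adding an adverse-event line to the current form would not settle which.

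At stake is how far the conclusion on adverse events can reach. The Concise Summary of Project says the pilot's data will be used to refine and power a full trial, which could inherit the same recording rule.

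**Working it through.** **1. Window against claim.** The form covers the encounter only (Sources of Research Material), and every item analysed goes onto that form first (Statistical Analysis Plan). The adverse-event comparison has no other stated source. Following the plan as written, an event that first appears after the patient leaves has no route into it. This step needs no arithmetic.

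**2. The plan's own figure.** Concise Summary of Project gives 33 encounters per group and 66 in total; 33 + 33 = 66 agrees. No event rate, power or margin is stated, so nothing further can be reproduced.

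**3. How often consecutive encounters differ in catheter.** There are 66 envelopes, half per arm, drawn without replacement (Randomization Procedure). Given the arm of one encounter, 65 envelopes remain, 33 of them for the other arm:

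P(next study encounter uses the other catheter) = 33/65 = 50.8%.

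This ignores the removal of patients after a second 20G failure, whose frequency is not given.

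**4. How many encounters are followed by another study form.** Each patient has exactly one last study encounter, so the number of encounters with no later study form equals the number of patients.

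| Patients | Source | No later study form | Followed by a study encounter | Of those, other catheter expected |
|---|---|---|---|---|
| 30 | Recruitment Methods and Consenting Process | 30/66 = 45% | 66 − 30 = 36 | 36 × 33/65 = 18.3 |
| 7 | Fewest possible under the cap of 10 (66/10 = 6.6, rounded up) | 7/66 = 11% | 66 − 7 = 59 | 59 × 33/65 = 30.0 |

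Between 11% and 45% of encounters therefore have no later study form on which a late event could be noted, even informally. Of the rest, about half are followed by a form that carries the other catheter.

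**5. What the form offers.** As reproduced, Appendix 1 has columns for alarms and comments but no visible adverse-event or site-inspection field. Nothing on it refers back to a previous encounter.

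**The case against.** The strongest reply is that a form confined to the current encounter omits late events in both arms alike. That narrows the scope of the safety comparison but does not move events between arms. This is right as far as it goes, and it leaves the narrowed scope standing.

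A reader might go further and infer that late events will be charged to the next visit's catheter, pulling the arms together and favouring the hoped-for result. If every late event were noted at a next study encounter and counted there, the apparent difference would be (32/65 − 33/65) = −1/65 of the true one. With assumed rates of 10% (20G) and 4% (18G), the arms would show (32 × 10% + 33 × 4%)/65 = 6.95% and (32 × 4% + 33 × 10%)/65 = 7.05%. The documents do not support this as the expected outcome, for three reasons:

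- They contain no attribution rule, so charging to the next catheter is only a possibility.
- The calculation needs every late event to be seen at a later study encounter, yet with 30 patients 45% of encounters have none.
- The rates and their direction are invented. The only text linking gauge to a site harm, in Background and Significance, associates scarring with the larger needle. In that direction, dilution would hide an advantage of the 20G catheter.

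Three further points stand:

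- Bruising, clotting and infection are listed as risks of blood sampling, which happens in both arms. Study procedure draws the sample from the procedure's access site, while the randomised catheter is at the return site. The plan therefore does not name these as harms of the compared catheters.
- A failed 20G encounter uses both catheters, so a simple link to the previous catheter is ambiguous there.
- This is a pilot whose Introduction frames safety around hemolysis, which is sampled at every encounter. Even at the assumed rates, 33 encounters would give about 3.3 and 1.3 events, too few for a firm conclusion.

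None of this supplies a later check or an attribution rule.

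**Conclusion.** The point holds in a limited form. It is certain from the text that adverse events appearing after the encounter have no planned route into the comparison, and that no rule links a late event to the encounter that preceded it. Misassignment between arms is possible, because a following study encounter has a 50.8% chance of using the other catheter, but it is not stated. The size and direction of any bias cannot be derived from the documents.

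The conclusion assumes that some return-site harms become visible only after the patient leaves. The 45% figure further assumes that all 66 encounters are used by the expected 30 patients. This is a worthwhile, inexpensive improvement and does not bear on the sample size.

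**What to change.** 1. Amend the sentence in Sources of Research Material that confines the form to the encounter.
2. Add one row to Appendix 1, completed at the start of the patient's next apheresis visit, whether study or standard of care, and before any new envelope is drawn. It records the condition of the previous return site, separately from the access site, and anything the patient reports since the last visit.
3. Link the row to the previous encounter's study number, date and randomised arm. Mark encounters in which both catheters were used because the 20G was replaced.
4. In the Statistical Analysis Plan, count these events under the previous encounter's randomised arm, and report by arm how many encounters lack the check.
5. If this is not adopted, restrict the safety conclusion explicitly to events observed during the procedure.

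The cost is a form revision, a wording change and about a minute at a visit the patient already attends. Checks will be missing for patients who do not return. Scarring may build up over several visits, so a single next-visit check cannot fully attribute it to one catheter.
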